10.3.3 Exploratory Efficacy

The exploratory efficacy variables include as follows. The Presence of Infection/Clinical signs of infection, Estimation of tissue types, Condition of target ulcer peri-wound skin, Need for administration of antibiotics and additional interventions, dressing wear time, pain on removal of dressing and at initiation of, and during, therapy. In addition, the impact of the device on aspects of daily living and satisfaction with device therapy will also be assessed. In the analyses detailed in this section, the Full Analysis Set will be used.

Presence of Infection / Clinical signs of infection

A Fishers Exact test will be used to test for a difference in the percentage of subjects with incidence of infection presenting during the 12-week treatment period between treatments, the corresponding 95% confidence intervals will also be presented.

The presence of infection and clinical signs of infection will be summarized at each assessment by treatment and wound type.

Need for administration of antibiotics and additional interventions

A Fishers Exact test will be used to test for a difference in the percentage of subjects requiring either the administration of antibiotic or additional interventions, between treatments. The corresponding 95% confidence intervals will also be presented.

The need for administration of antibiotics and additional interventions will be summarized at each assessment and overall by treatment and wound type.

Dressing wear time

The linear regression model will be fitted to the average wear time per subject. Treatment, center, wound strata, baseline ulcer area and exudate level will be included in the initial model.

The difference between the two treatments in terms of average wear time per subject (treatment parameter estimate) will be presented along with the 95% confidence intervals. If residuals are found to be not normally distributed then non-parametric bootstrapping will be applied. Further information is included in the SAP.

The average wear time per subject (at a subject level) will be summarized by treatment for each of the covariates detailed in the previous paragraph. The duration of dressing wear (at a dressing level) will also be summarized by treatment, and: center, wound strata, level of exudate at the previous assessment and ulcer area (categorized) at the previous assessment.

Impact of the device on aspects of daily living and satisfaction with device therapy

All responses to the exit survey will be summarized by treatment and by individual tNPWT device. In addition, where appropriate, a Cochran-Mantel-Haenszel test will be used to test for a difference in subject response between treatments for individual survey questions.

Remaining exploratory endpoints, including the estimation of tissue types present, condition of peri-wound skin and the pain on removal of dressing and at initiation of, and during, therapy, will be summarized by assessment and treatment.

CONFIDENTIAL DOCUMENT
This document contains confidential information, which is the property of Smith & Nephew, Inc. Do not copy, disclose, or circulate without written authorization from the appropriate Smith & Nephew personnel

Other Planned Analysis

At minimum, all data collected will be summarized and listed by treatment; where appropriate data collected will also be summarized by tNPWT device. Additional subsets for summaries may be utilized as a result of the analyses relating to the primary and secondary objectives.

10.4 SAFETY

All safety analyses and summaries will be conducted using the Safety Population. Unless otherwise stated, all safety summaries will be presented by treatment and wound type (DFU or VLU) and overall. All safety analyses will also be separated by tNPWT device.

Extent of Exposure

The duration of treatment with NPWT will be summarized.

Adverse Events

Adverse events will be coded and grouped by system organ class using the Dictionary for Medical Drug Regulatory Activities (MedDRA).

The number of subjects reporting: adverse events, serious adverse events, severe adverse events, investigational device related adverse events, a serious investigational device related adverse event, an unexpected adverse event and a serious unexpected adverse event. In addition, for each adverse event, the following will be summarized: severity, treatment, NPWT usage, the relationship to the investigational device, the possible cause if related, outcome and duration of the resolved adverse events and the duration of the adverse events at trial discontinuation.

The proportion of subjects with a device-related adverse event will be compared between treatments using Fisher's exact test. In addition, the percentage of serious device related adverse events and the corresponding 1-sided upper 95% confidence limit will be detailed assuming a Poisson distribution for serious device related adverse events separately for each treatment.

The number and proportion of subjects reporting treatment-emergent adverse events split by treatment separately by system organ class, and preferred term will be summarized by:

CONFIDENTIAL DOCUMENT
This document contains confidential information, which is the property of Smith & Nephew, Inc. Do not copy, disclose, or circulate without written authorization from the appropriate Smith & Nephew personnel

1. Their relationship with the investigational device (not related or related). If the relationship is missing, the adverse event will be assumed to be treatment-related and a footnote will be added to the table. If a subject experiences more than one preferred term within a system organ class, then the relationship at the system organ class level for that subject will be reported according to their most related relationship for each preferred term.
2. The severity of the adverse event (mild, moderate or severe).
3. Whether or not the adverse event is serious
4. The adverse event outcome.
5. Whether or not the adverse event is expected or unexpected.

Clinical Laboratory Evaluations

The subject blood biochemistry and hematological parameters (including the numbers of subjects that are below, within and above the normal ranges) at screening visit will be summarized.

Vital Signs, Physical Findings

The subject blood pressure (systolic and diastolic), pulse and temperature at the screening visit will be summarized.

11. SAMPLE SIZE JUSTIFICATION

The study is intended to test for non-inferiority in the percentage change in target ulcer area between PICO and tNPWT over a 12-week treatment period. During a review of five previous studies with venous leg ulcer and diabetic foot ulcer, with treatment of PICO or tNPWT, the mean percentage change in ulcer area was found to be approximately between 47-62%, in cases where it was considered an appropriate measure, the standard deviation ranged approximately between 21-24.5%. Using a non-inferiority margin of 12.5%, a sample size of 128 subjects will provide 80% statistical power at the (cumulative) 0.025 one-sided significance level assuming a weighted average mean healing of 60% with a worst case standard deviation of 24.5%. To allow for a 20% drop out rate throughout the 12-week treatment period, a total of approximately 160 subjects (80 per treatment) will be randomized.

The sample size randomized will include a minimum of 100 VLU to allow for a minimum of 70% power for VLU-only analysis using the above assumptions.

An interim analysis (built into the sample size) of key variables will take place after approximately 50% of target recruitment (80 subjects completed) with the stipulation that the interim will contain at least 40 VLU and 20 DFU. The interim analysis will contain a check for efficacy with an alpha spend of 0.002. A non-binding look for futility will also be performed at the same time point. The Lan and DeMets (1983) “Pocock” spending function will be used²⁴. If the efficacy boundary of 2.963, using the Z scale is exceeded ($Z > 2.963$) a recommendation will be made to terminate the trial on the basis of efficacy. Alternatively, if the futility bound of 0.559 using the Z scale is crossed ($Z < 0.559$) it will be recommended to terminate the trial prematurely due to lack of efficacy (futility). Further details regarding the stopping criteria, including the corresponding values on the p-value scale to be used in circumstances where distributional assumptions do not hold, can be found in the SAP.

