7. SUBJECTS

7.1 SUBJECT POPULATION

A total of approximately 160 subjects, presenting with a lower extremity ulcer (VLU or DFU) will be recruited at approximately 15 investigational centers in the United States and Canada, but potentially including investigational centers located in the United Kingdom and European Union. Additional sites may be added, if necessary to meet recruitment goals. As a restriction within the total of 160 subjects, a minimum of 46 subjects presenting with a DFU will be recruited along with minimum of 100 subjects presenting with a VLU will be recruited, the remainder of recruitment will comprise of subjects with either ulcer type.

An interim analysis will be performed after 80 subjects have completed the study, including a minimum of 40 VLU and 20 DFU, at which point a recommendation may be to stop the study prematurely due to either efficacy or futility. The stopping criteria are detailed in the Statistical Analysis Plan (SAP).

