3. STATISTICAL CONSIDERATIONS

3.1 DETERMINATION OF SAMPLE SIZE

The study is intended to test for non-inferiority in the percentage change in target ulcer area between PICO and tNPWT over a 12-week treatment period. During a review of five previous studies with venous leg ulcer and diabetic foot ulcer, with treatment of PICO or tNPWT, the mean percentage change in ulcer area was found to be approximately between 47-62%, in cases where it was considered an appropriate measure, the standard deviation ranged approximately between 21-24.5%. Using a non-inferiority margin of 12.5%, a sample size of 128 subjects will provide 80% statistical power at the (cumulative) 0.025 one-sided significance level assuming a weighted average mean healing of 60% with a worst case standard deviation of 24.5%. This was calculated using EAST 6. To allow for a 20% drop out rate throughout the 12-week treatment period, a total of approximately 160 subjects (80 per treatment) will be randomized.

The sample size randomized will include a minimum of 100 VLU to allow for a minimum of 70% power for VLU-only analysis using the above assumptions.

An interim analysis (built into the sample size) of key variables will take place after approximately 50% of target recruitment (80 subjects completed) with the stipulation that the interim will contain at least 40 VLU and 20 DFU. A recommendation may be made at this point to stop the trial prematurely due to efficacy or futility.

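### The 70% power stated for the VLU-only analysis omits the plan's own 20% dropout; 100 randomised VLU give about 61–63%

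*Protocol*

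**What the plan says.** Protocol Section 11 sets out the design: "The study is intended to test for non-inferiority in the percentage change in target ulcer area between PICO and tNPWT". Its inputs are given as "Using a non-inferiority margin of 12.5" per cent and "with a worst case standard deviation of 24.5" per cent. For 128 subjects it claims "80% statistical power at the (cumulative) 0.025 one-sided significance level". It then adds: "To allow for a 20% drop out rate throughout the 12-week treatment period", about 160 subjects are to be randomised. The Protocol synopsis confirms that the 128 are subjects who complete the study.

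The next paragraph of Section 11 makes the VLU statement: "The sample size randomized will include a minimum of 100 VLU to allow for a minimum of 70% power for VLU-only analysis". SAP 3.1 has the same sentence, including the link to the preceding inputs: "to allow for a minimum of 70% power for VLU-only analysis using the above assumptions". No separate dropout allowance is given for the VLU figure.

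Three other provisions bear on how many VLU subjects can be analysed:

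- Protocol 7.1 counts the 100 VLU within the total of 160 and adds that "a minimum of 46 subjects presenting with a DFU will be recruited".
- Protocol 9.2.1 does not replace subjects who drop out after randomisation.
- Protocol 10.3.1 and SAP 4.9 run the primary analysis on the Per Protocol Population and repeat it on the Full Analysis Set.

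**The concern.** Two power statements a few lines apart use different denominators. The overall one is computed on completers and then inflated to a randomised number. The VLU one gives a power directly for a randomised number. If 20% of randomised subjects are expected to be lost overall, the same loss should be expected among the VLU subjects unless the plan says otherwise, and it does not.

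The 70% figure is the plan's stated reason for the 100-VLU quota. If the devices are truly equivalent, a reader relying on it would expect a VLU-only analysis to miss non-inferiority at most 30% of the time. If the real figure is nearer 38%, an inconclusive VLU result says less against PICO in VLU than the stated power suggests.

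**Working it through.** **Inputs**

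- Margin 12.5 and SD 24.5 percentage points (Protocol 11, SAP 3.1).
- One-sided alpha 0.025, z = 1.960 (Protocol 11). The final analysis uses a 95.4% two-sided interval, i.e. one-sided 0.023, z = 1.995 (Protocol 10.3.1, SAP 4.9).
- 1:1 allocation; 20% dropout.
- True difference 0. This is an assumption: the plan gives a single mean of 60% and no difference between arms.
- The same 20% dropout in VLU as overall. This is also an assumption: the plan gives no rate by ulcer type.

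**Formula**

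For N evaluable subjects in total, split equally:

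Power = Φ(drift − z), where drift = 12.5 / (24.5 × √(4/N)).

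**Step 1: reproduce the headline figure**

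N = 128: drift = 12.5 / (24.5 × 0.1768) = 2.886. Power is 82.3% (z = 1.960) or 81.4% (z = 1.995). Using the t distribution at 0.023 it is 80.7%. With the two-look boundaries (2.963 for efficacy, 0.559 for futility) it lies between 79.6% and 82.4%, depending on interim timing, final critical value and whether futility stopping is applied. The stated 80% reproduces, and 128 / 0.8 = 160 exactly. This is the right model for the plan.

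**Step 2: find what the 70% corresponds to**

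N = 100: drift = 12.5 / (24.5 × 0.2) = 2.551. Power is 72.3% or 71.1% (t: 71.4% or 70.2%; two-look variants 69.2–72.4%). The stated minimum of 70% therefore matches 100 evaluable VLU subjects, with no dropout.

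**Step 3: apply the plan's dropout**

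100 × 0.8 = 80 completers, 40 per arm. Drift = 12.5 / (24.5 × 0.2236) = 2.282. Power is 62.6% or 61.3% (t: 61.6% or 60.2%; two-look variants 59–63%).

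**Step 4: the most VLU the quotas allow**

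160 − 46 = 114 VLU randomised, and 114 × 0.8 = 91.2 completers. Drift = 2.436. Power is 68.3% or 67.0%.

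**Step 5: what 70% would need**

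N = 4 × [24.5 × (z + 0.524) / 12.5]². This gives 94.8 (z = 1.960) or 97.6 (z = 1.995) completers. Dividing by 0.8 gives 118.6 or 122.0, i.e. about 119–122 VLU randomised. Equivalently, with 100 randomised, 70% survives only if about 2–5% are lost.

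| VLU randomised | Evaluable | Power, z = 1.960 | Power, z = 1.995 |
|---|---|---|---|
| 100, no dropout | 100 | 72.3% | 71.1% |
| 100, 20% dropout | 80 | 62.6% | 61.3% |
| 114, 20% dropout | 91.2 | 68.3% | 67.0% |

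**The case against.** The strongest reply is that the number analysed is not fixed at 80. The Per Protocol definition (Protocol 10.1, SAP 4.4) is not limited to completers: it keeps subjects who stop treatment after about nine weeks, and those whose ulcer closes at any time. Last observation carried forward supplies their endpoint. The Full Analysis Set needs only treatment and one post-baseline visit, so it could hold close to 100 VLU subjects, with about 71–72% power. This is correct as far as it goes. But the Per Protocol set also removes significant protocol deviations, so its size could fall on either side of 80. The plan itself deducts the full 20% for its headline figure, and the VLU figure should follow the same convention.

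Other points:

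- *Dropout may not be one of the assumptions referred to.* On that reading the sentence gives power for 100 analysed VLU. The sentence calls the 100 randomised, however, and it directly follows the dropout step.
- *The SD is a worst case.* With the plan's lower value of 21, 80 completers give about 75–76%. The 70% is claimed under the stated assumptions, which use 24.5.
- *The total is approximate.* A modest overrun could admit 119–122 VLU alongside 46 DFU (165–168 in all). The plan does not provide for this.
- *The 61.3% carries the 95.4% interval over to a VLU-only analysis.* No section says so. Without it the figure is 62.6%.
- *No VLU-only test is specified.* Wound type is a covariate and subgroup analyses are only permitted, so no decision rule depends on this power. That stands, and it limits the consequence. It does not make the figure right.

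**Conclusion.** The concern holds. Under the plan's own margin, SD, alpha and dropout, and assuming no true difference and equal dropout across ulcer types, 100 randomised VLU give about 61–63% power on a completer basis, not at least 70%. The shortfall is about 7 to 9 percentage points. The chance of missing non-inferiority in VLU when the devices are equivalent is about 37–39%, against the 30% at most that the plan implies. The conclusion does not depend on the formula: t-based and two-look calculations give the same or slightly lower power. No VLU count within a total of 160 and the DFU quota reaches 70% at 20% dropout.

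This is an error in a stated design property of a subset analysis. The primary test, the overall 80% power and the enrolment target are unaffected.

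**What to change.** In Protocol Section 11 and SAP 3.1, replace the VLU power sentence with wording such as:

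> *A minimum of 100 randomised VLU (about 80 completers after 20% dropout) gives about 61–63% power for the VLU-only analysis, which is supportive.*

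The cost is one sentence in each document and a less favourable stated figure. Enrolment, quotas and analyses stay as they are.

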12. ADVERSE EVENTS

12.1 GENERAL INFORMATION

An Adverse Event (AE) is any untoward medical occurrence temporally associated with the use of an investigational medicinal product or device, whether or not considered causally related to that product/device. An AE can be any unfavorable and unintended sign (for example, an abnormal laboratory finding), symptom, or disease.

An Adverse Device Effect (ADE) is an adverse event that, in the opinion of the investigator, is related to the device.

12.2 SERIOUS ADVERSE EVENTS

An adverse event is considered “serious” if, in the view of either the investigator or the sponsor, it

- Results in death
- Is life-threatening (*NOTE*: The term “life-threatening” in the definition of “serious” refers to an event/reaction in which the subject was at risk of death at the time of the

event/reaction; it does not refer to an event/ reaction which hypothetically might have caused death if it were more severe)

- Requires in subject hospitalization or results in prolongation of existing hospitalization
- Results in persistent or significant incapacity or substantial disruption of the ability to conduct normal life functions
- Is a congenital anomaly/birth defect
- Is a medically important event or reaction

Medical and scientific judgment should be exercised in deciding whether other situations should be considered serious such as important medical events that might not be immediately life-threatening or result in death or hospitalization but might jeopardize the subject or might require intervention to prevent one of the other outcomes listed in the definition above. Examples of such events are intensive treatment in an emergency room or at home for allergic bronchospasm, blood dyscrasias, or convulsions that do not result in hospitalization; or development of drug dependency or drug abuse.

A DevD is a malfunction of the device that could present a risk to the subject, caregiver, or bystander.

12.3 NON-SERIOUS ADVERSE DEVICE EFFECTS

A nonserious adverse event is defined as a change from baseline (pre-treatment) in a subject's medical health that is not life-threatening, does not require hospitalization, does not prolong a current hospitalization and is not disabling. Nonserious adverse device effects must be reported to Smith & Nephew Inc., by use of an Adverse Event Form.

All nonserious adverse events must be reported in the subject's source documents; AE associated with the target ulcer or related to the test article must be recorded on an Adverse Event Form regardless of whether or not they are considered to be related to the test article

CONFIDENTIAL DOCUMENT
This document contains confidential information, which is the property of Smith & Nephew, Inc. Do not copy, disclose, or circulate without written authorization from the appropriate Smith & Nephew personnel

12.4 REPORTING AND EVALUATION AE AND SAE

AE associated with the target ulcer and target leg and all SAE, SADE, UADE and ADE of any kind will be recorded in the AE eCRF; DevD will be recorded on an eCRF specifically designed for recording such events. The Investigator will evaluate all SAE and target ulcer and target leg AE for relationship to the device and severity. AE judged to be device related and all SAE will be entered into the eCRF. All device-related AE, SADE, SAE and DevD will also be reported in the SAE form available in the Regulatory Folder and faxed to the Clinical Study Manager, Medical Monitor, and Medical Reviewer within 24 hours of knowing about the event (Figure 12.4-1). Target ulcer and target leg AE judged not related to the device will be entered into the safety database within 48 hours of becoming aware of the event. All SAE and device related AE will be reviewed by the Medical Monitor and the Medical Reviewer to determine which, if any, meet expedited reporting criteria.

All events requiring expedited reporting will be forwarded to Regulatory by the Medical Reviewer for further processing.

[figure not shown]

Figure 12.4-1: Evaluation of an Adverse Event by the Investigator

All DevD are considered to be serious and will be reported within 24 hours to the Sponsor

When new significant follow up information is obtained as well as when the outcome of an event is known, the Investigator must update the appropriate eCRF forms with the additional information. In certain cases, Smith & Nephew Inc. also may request a letter from the Investigator that summarizes the events related to the case.

The Medical Monitor and Medical Reviewer will review and classify all devices related AE and all SAE as follows, based on FDA 21 CFR §812.40:

Adverse Device Effect (ADE) Adverse event is judged to be device related, but is not serious and does not meet expedited reporting

Unanticipated Adverse Device Effect (UADE) Any serious adverse event that is caused by or related to the investigational device, not previously identified in nature, severity or degree; this meets the criteria for expedited reporting and the Sponsor will forward to the Regulatory group for submission to the FDA within 15 days of the initial report from the site.

Serious Adverse Event (SAE) A serious adverse event that is not related to the use of the device does not meet the criteria for expedited reporting.

12.5 ADVERSE DEVICE EFFECT SEVERITY AND CAUSALITY ASSESSMENT

The severity of all AE, will be assessed by the Principal Investigator and should be classified as mild, moderate, or severe. The classification should be based on the following definitions:

- **Mild** – An event is mild if the subject is aware of, but can easily tolerate the sign or symptom;
- **Moderate** – An event is moderate if the sign or symptom results in discomfort significant enough to cause interference with the subject's usual activities;
- **Severe** – An event is severe if the sign or symptom is incapacitating and results in the subject's inability to work or engage in their usual activities.

In addition, the Principal Investigator will determine causality according to the following definitions:

- **Not Related** – An AE is considered to be not related to the use of the device when the effect is DEFINITELY UNRELATED or UNLIKELY to have any relationship to the use of the device;
- **Related** – An AE is considered to be related to the use of the device when there is a POSSIBLE, PROBABLE, or DEFINITE relationship between the AE and the use of the device.

All ADE and UADE are considered to be related to the use of the device.

